COVID-19 Vaccinations With a Sweepstakes

NCT04951310

6/7/2021

COVID-19 Lottery Study Pre-Registration

1) Have any data been collected for this study already? No.

2) What's the main question being asked or hypothesis being tested in this study?

We will measure the effectiveness of a COVID-19 vaccination sweepstakes by analyzing COVID-19 vaccination data from the City of Philadelphia and neighboring regions. The sweepstakes will award multiple prizes every two weeks for at least six weeks. Half of the prizes will be awarded to Philadelphia residents in "selected" zip codes that are randomly selected from a list of 20 under-vaccinated zip codes in the city. selected zip codes will be announced two weeks prior to each drawing. The other half of prizes will be awarded to Philadelphia residents in the remaining zip codes in Philadelphia. We will examine (1) the effect of the lotteries (and accompanying attention that they bring to the vaccination process) on Philadelphia resident vaccination rates relative to people living in neighboring counties and cities and (2) the effect on vaccination rates of selected zip code residents compared to residents from other Philadelphia zip codes that were eligible for this designation ("potentially selected").

3) Describe the key dependent variable(s) specifying how they will be measured.

The primary outcome is the weekly vaccination rate for residents receiving a first dose of a COVID-19 vaccination in each zip/county/city as measured by local health departments and, for residency, as measured by the Census or other official sources.

(Rate = Total residents receiving a first dose that week / Total residents in that zip/county/city code as measured by the Census or other official sources, at the most recent data available for all geographies of interest. This source as of pre-registering is the American Community Survey 2019.)

4) How many and which conditions will participants be assigned to?

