We will partner with the City of Philadelphia to launch a COVID-19 vaccination sweepstakes that will be conducted for at least 6 weeks. The city will be included in the "treatment" condition. Within the city, we will include two pools: a "potentially selected" zip code pool (including the 20 zip codes with the lowest per capita vaccination rates as of May 27, 2021) and a pool with the remaining zip codes. At the start of each two-week period, we will randomly draw one "selected" zip code from our list of 20 under-vaccinated zip codes in the city. Half the prizes in each category will go to those in the "selected" zip code.

[figure not shown]
Our differences-in-differences analysis will compare weekly first-dose COVID-19 vaccination rates in each of the three "selected" zip codes (drawn from 20 "priority" zip codes) against the "potentially selected" zip codes that were not selected. We will also compare COVID-19 vaccination rates in all of Philadelphia (Philadelphia county) with vaccination rates in neighboring Pennsylvania counties (Bucks County, Delaware County, and Montgomery County, as per Roberto et al. 2019) and in one comparison city (Baltimore, as a comparable and nearby city and as per Roberto et al. 2019) over the same time period.

5) Specify exactly which analyses you will conduct to examine the main question/hypothesis. We will conduct 3 main analyses:

1. Comparing across cities

To analyze the effect of living in Philadelphia as compared with neighboring counties, we will run a standard difference-in-differences model for weekly COVID-19 vaccination rates by county in the weeks leading up to, during, and after the intervention period. We will include data from May 2, 2021 through August 14, 2021 in this analysis (5 weeks of pre-intervention, 6 weeks of intervention, and 4 weeks of

post-intervention). The analysis will begin by showing a graphical event study representation of the results as follows (graph uses hypothetical data):

Hypothetical Figure 1: (linked http://bit.ly/BCFGPhilVaxPreReg)

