The graph above is created by regressing the weekly first-dose COVID-19 vaccination rate for each "potentially selected" zip code (20 total) on zip code fixed effects, week fixed effects, and indicators for pre-treatment and post-treatment effects (as described, for example, in Cunningham 2021). This plot allows us to see the timing/dynamics of the treatment effect and also provides evidence regarding the parallel-trends assumption that is always made in a diff-in-diff analysis by checking for pre-treatment differences in trends.

In addition to the graphical analysis above, we will also produce the standard diff-in-diff 2x2 estimate by taking the average vaccination rate pre-treatment for each zip code and the average vaccination rate during the treatment period for each zip code and regressing these DVs on Zip Code Indicators, a Treatment Indicator, and a selected Zip Code*Treatment indicator. The coefficient on the interaction term will be our preferred estimate of the overall effect of each lottery's impact on each of the "selected" zip codes relative to "unselected" zip codes (across the full treatment period, this will be 17 remaining zip codes).

There will be three different figures above for each of the 2-week lottery periods (one figure for each of the 3 "selected" zip codes). After showing the effects separately for each of the 3 "selected" zip codes, we can also do a pooled analysis where we combine/average the results across the 3 "selected" zip code analyses. To do this, we can stack the data from the 3 studies and produce just one figure like the one above where we show the same results relative to week 0 of the event window. To produce the final overall effect of the lotteries impact on the "selected" zip code, we will regress the weekly vaccination rate for each zip code on zip code fixed effects, week relative to treatment fixed effects (1 week before treatment, 2 weeks before treatment, etc.), and a "selected" zipcode*treatment indicator that equals one when the "selected" zip code was in the treatment period.

6) Describe exactly how outliers will be defined and handled, and your precise rule(s) for excluding observations.

No outliers will be excluded.

7) How many observations will be collected or what will determine sample size?

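### Should the zip-code estimates adjust for the pre-period rate instead of using difference-in-differences?

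*Combined protocol and SAP*

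**What the plan says.** Section 3 defines the outcome as "Rate = Total residents receiving a first dose that week / Total residents in that zip/county/city code". Section 4 makes the zip-code comparison a randomised one: "At the start of each two-week period, we will randomly draw one" zip code from a list of 20.

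In section 5, analysis 3, the preferred per-lottery estimate starts with "taking the average vaccination rate pre-treatment for each zip code and the average vaccination rate during the treatment period for each zip code". The model step that follows is "regressing these DVs on Zip Code Indicators, a Treatment Indicator, and a selected Zip Code*Treatment indicator". The comparison group is the zip codes that are never drawn: "across the full treatment period, this will be 17 remaining zip codes".

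For the pooled effect, "we will regress the weekly vaccination rate for each zip code on zip code fixed effects, week relative to treatment fixed effects", together with an indicator for a selected zip code inside its own treatment window. Section 5 (analysis 1) and section 7 run the data from May 2 to August 14, which is 5 + 6 + 4 = 15 weeks. The pooled paragraph does not say whether the post-treatment weeks stay in the stack.

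Neither zip-code model has the pre-period mean as a covariate. The documents give no between-zip variance, pre/during correlation or power figure.

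**The concern.** With zip-code indicators and two periods, the interaction coefficient is the selected zip code's change minus the average change in the controls. If the true slope of the treatment-period rate on the pre-period rate is below 1, part of the drawn zip code's baseline gap stays in the estimate as chance error.

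A slope below 1 is plausible. Each resident can contribute only one first dose and the denominator is all residents, so zip codes with high early uptake may fall faster and the gaps may close. Each lottery rests on one selected zip code, so precision is scarce. Regressing each zip code's treatment-period mean on its pre-period mean and the selected indicator would use data already in hand, and the random draw makes it valid without a parallel-trends assumption. It looks like precision given away for nothing.

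**Working it through.** **Inputs.** From the documents: 20 zip codes, 3 drawn, 17 controls, 15 weeks, two-week lottery windows. Assumed, because the documents are silent: k = between-zip SD before / SD during, r = their correlation, and every variance used in the simulations.

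**1. Per-lottery estimate, closed form.** For one selected zip code against m controls, the ratio of variances (planned over adjusted; above 1 favours adjusting) is

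[(1 + k² − 2rk) / (1 − r²)] ÷ [1 + 1/(m − 3)].

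The divisor is the expected cost of estimating the slope, taking baseline rates as roughly normal. With m = 17 it is 15/14, about 7%.

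| k | r | Calculation | Ratio |
|---|---|---|---|
| 1 | 0.5 | (1.00/0.75) × 14/15 | 1.24 |
| 1 | 0.8 | (0.40/0.36) × 14/15 | 1.04 |
| 1 | 0.9 | (0.20/0.19) × 14/15 | 0.98 |
| 1 | 0.95 | (0.10/0.0975) × 14/15 | 0.96 |
| 0.8 | 0.8 | (0.36/0.36) × 14/15 | 0.93 |
| 1.25 | 0.8 | (0.5625/0.36) × 14/15 | 1.46 |

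- With equal SDs the ratio is [2/(1 + r)] × 14/15, so break-even is r = 28/15 − 1 = 0.867.
- For k above 1 the lowest ratio over all r occurs at r = 1/k and equals k² × 14/15. Adjusting therefore wins at every correlation once the SD during falls below √(14/15) = 0.966 of the SD before, a shrinkage of 3.4%. At 10% shrinkage the ratio is at least (1/0.81) × 14/15 = 1.15; at 20%, (1/0.64) × 14/15 = 1.46.
- The worst case is 14/15 = 0.93, a standard error larger by √(15/14) − 1 = 3.5%.

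When zip codes decline at different rates (SD 2 points), simulated per-lottery ratios were about 0.91 to 1.27 for mean declines of 0 to 5% a week, so they lie on both sides of 1.

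**2. Pooled estimate: the reference weeks decide.** Number the weeks 1 to 15. The lottery windows are weeks 6–7, 8–9 and 10–11, with midpoints 6.5, 8.5 and 10.5. If gaps drift steadily, the error from a drawn zip code's gap is proportional to the distance between the window midpoint and the mean reference week.

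| Reference weeks | Lottery 1 | Lottery 2 | Lottery 3 | Sum of squares |
|---|---|---|---|---|
| Fixed, weeks 1–5 (mean 3) | 3.5 | 5.5 | 7.5 | 98.75 |
| Five weeks before each draw | 3.5 | 3.5 | 3.5 | 36.75 |
| All 13 other weeks (means 8.23, 7.92, 7.62) | −1.73 | 0.58 | 2.88 | 11.65 |

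With all weeks in, the drift part of the variance is 98.75/11.65, about 8.5 times smaller than with the fixed pre-period, because weeks on both sides of the window offset each other. Week-to-week noise falls too: in units of the weekly noise variance it is 1/2 + 1/13 = 0.577 against 1/2 + 1/5 = 0.700, a ratio of 0.82. With the slope cost and no drift that gives roughly 0.82 × 14/15 = 0.77 in favour of the planned model.

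**3. Pooled estimate, simulated.** Assumed: 2.5% of residents a week at the start, zip spread 10–40%, weekly noise 10–15%, true effect 0. Ratios are planned pooled regression over fixed-baseline adjustment.

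| Decline per week | Pre and treatment weeks only | All 15 weeks |
|---|---|---|
| 0% | 0.93–1.02 | 0.75–0.80 |
| 3% | 1.16–1.74 | 0.75–0.83 |
| 5% | 1.28–3.33 | 0.79–0.97 |
| 7% | 1.57–5.86 | 0.81–1.21 |

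Repeat runs with all weeks in gave 0.73–0.93 for declines of 0 to 5%; the widest range in any run was 0.67–1.28. With zip-specific declines the all-weeks ratio was 0.24–0.52. If post weeks are dropped and the baseline is the five weeks before each draw, the gain of adjusted over averaged 2x2 estimates is modest at slow declines: 1.00–1.09 at 2% a week and 1.04–1.26 at 3%.

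**The case for a change.** The strongest argument for changing is asymmetry. For the per-lottery estimate the expected loss from adjusting is capped at about 7% in variance, while the gain is at least 15% if gaps shrink by 10% and grows from there. On a normal approximation with two-sided 0.05, an effect with 80% power under the plan would have about 85% at a ratio of 1.15 and 77% at 0.93. The change costs only wording, and it has to be made in advance, because picking the estimator after seeing the data would undo the benefit.

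This stands for the per-lottery estimates. It does not carry over to the pooled one. The cap fails there: with post weeks in, replacing the planned model usually costs far more than 7%. Against that, section 8 anticipates a possible fall in vaccination after the lotteries, and such a fall or any carry-over would distort a reference that includes post weeks. That is a question about the window, separate from the baseline slope.

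The plan also gains something by keeping one method. The event-study plots, the 2x2 estimates and the search for a later reversal in section 8 share a scale. Adjusting only the treatment-period effect would put an effect and its reversal on different estimators.

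**Conclusion.** The algebra behind the concern is right: the per-lottery estimate fixes the slope at 1, and adjustment is valid under the random draw (taken as equal probability without repeats, which 17 remaining zip codes implies). No change follows, for three reasons.

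- There is no bias to remove. In the simulations both methods had mean error of at most 0.01 points a week.
- The sign of the precision gain is unknown. Per lottery, adjusting wins if gaps shrink by more than about 3 to 4% or if the pre/during correlation is moderate; otherwise it costs up to about 7% in variance. The documents give no variances to settle this, and shrinking gaps are an assumption.
- For the pooled estimate no gain can be claimed. If all weeks enter, the planned model is usually the more precise one, provided the post weeks carry no harvesting or carry-over.

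Which weeks form the pre-period for lotteries 2 and 3 is a detail that analysts can settle from the relative-week set-up. A baseline-adjusted version of the per-lottery estimates would be a harmless optional sensitivity analysis, but the plan is sound without it. The argument does not reach the city and county comparisons, where treatment was not randomised.

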No need to justify the decision, but be precise about exactly how the number will be determined. Weekly vaccination totals by zip code in Philadelphia will be collected from the Philadelphia department of public health. Weekly vaccination totals by county will be collected from the CDC. For each region of interest we will include weekly vaccination data from May 2nd through August 14th (for 5 weeks prior to the announcement of the sweepstakes, during the entire sweepstakes, and for 4 weeks after the conclusion of the sweepstakes.)

8) Anything else you would like to pre-register?

Assuming we find positive effects from the treatment, the increased vaccinations could be a result of persuading people who would not have otherwise been vaccinated to become vaccinated or a result of causing people who were eventually going to be vaccinated to move up their vaccination date. If the latter is true, we may see a reduction in vaccination rates in the post-treatment period. This is what in economics has been referred to as a "harvesting" effect where you are simply causing intertemporal substitution for when people perform an action like vaccination. The graphs discussed above will allow us to look for this intertemporal substitution effect by seeing if the dots are less than 0% in the post-treatment period and a similar analysis as listed above will allow us to estimate the magnitude of this substitution.

Assuming we are able to collect data on awareness of the lottery through our partner research organizations we also intend to run a mediation analysis with "awareness" as a mediator.

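### The pooled zip-code regression treats post-lottery weeks as untreated reference weeks, so any post-lottery change in a selected zip code shifts its headline estimate

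*Combined protocol and SAP*

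**What the plan says.** All references are to the combined protocol and SAP.

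- **Pooling (item 5, analysis 3, Comparing across zip codes).** Pooling is first offered as an option: "we can also do a pooled analysis where we combine/average the results across the 3" selected-zip analyses. The summary regression is then described without that hedge, opening with "To produce the final overall effect of the lotteries impact on the" selected zip code.
- **The pooled model.** Weekly rates are regressed on zip effects, "week relative to treatment fixed effects (1 week before treatment, 2 weeks before treatment, etc".), and one "zipcode*treatment indicator that equals one when the 'selected' zip code was in the treatment period". There is no selected-by-post term. The listed examples of relative weeks are all pre-treatment, and no end of the event window is given.
- **The per-zip estimate (same section).** The preferred 2x2 estimate for each lottery is built by "taking the average vaccination rate pre-treatment for each zip code and the average vaccination rate during the treatment period for each zip code". Post-lottery weeks do not enter it.
- **Data (item 7).** For every region "we will include weekly vaccination data from May 2nd through August 14th". Item 5, analysis 1 splits this into 5 weeks before, 6 during and 4 after the intervention.
- **Post-lottery behaviour (item 8).** If doses are only brought forward, "we may see a reduction in vaccination rates in the post-treatment period". The plan relies on the event-study graphs to show this and adds that "a similar analysis as listed above will allow us to estimate the magnitude of this substitution", without giving a model.

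**The concern.** The indicator is 1 for the selected zip code in its two lottery weeks and 0 in every other week. The reference for the lottery weeks is therefore a mixture of weeks before and weeks after. The relative-week effects do not repair this: they are shared with the unselected zip codes and absorb only common changes, not a change specific to the selected zip code.

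The lottery-period effect is then misstated whenever the selected zip code behaves differently afterwards. A harvesting dip lowers the reference and inflates the coefficient, so the mechanism the authors want to detect would enlarge their summary figure. A gain that persists raises the reference and shrinks it. The documents do not show which is likelier.

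There is also an inconsistency. The pooled figure is meant to combine the three per-zip results but uses a different reference period, so it can differ from their average for reasons unrelated to what happened during the lotteries.

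**Working it through.** **Inputs.** May 2 to August 14 inclusive is 105 days = 15 weeks, which reproduces the plan's 5 + 6 + 4. Three consecutive two-week lotteries fill the 6 weeks, so they start in weeks 6, 8 and 10. Never-selected controls: 20 - 3 = 17. The documents give no effect sizes, so every post-lottery scenario below is assumed.

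**Reference weeks for each selected zip code, all 15 weeks stacked**

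| Lottery | Pre | Lottery | Post | Post share of weeks coded 0 |
|---|---|---|---|---|
| 1 | 5 | 2 | 8 | 8/13 = 0.615 |
| 2 | 7 | 2 | 6 | 6/13 = 0.462 |
| 3 | 9 | 2 | 4 | 4/13 = 0.308 |
| Total | 21 | 6 | 18 | 18/39 = 0.4615 |

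**Formula.** Let d be the true weekly effect during the lottery and s the mean post-lottery shift, both relative to unselected zip codes. For one lottery, estimate = d - s × post/(pre + post). Each lottery has 2 treated and 13 untreated weeks, so the three count equally and, for a common s, the pooled estimate is d - 0.4615s.

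**Scenarios, all weeks**

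| Assumed post-lottery behaviour | Pooled estimate |
|---|---|
| No change | 1.00d |
| s = -0.25d | d + 0.4615 × 0.25d = 1.115d |
| s = +0.25d (25% carry-over) | d - 0.4615 × 0.25d = 0.885d |
| s = +d (full carry-over) | 0.538d |
| Half of the two-week gain lost evenly | 1.077d |
| All of the two-week gain lost evenly | 1.154d |

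In the last two rows, the loss of a fraction f of the gain 2d is spread over the post weeks, so s = -2fd/post. The bias in each lottery is then (post/13) × (2fd/post) = 2fd/13. In the final row the net gain is zero.

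**Other windows (assumed).** With -5 to +5 there are 5 pre and 4 post weeks: multiplier -4/9 = -0.444. With -5 to +3 there are 5 and 2: -2/7 = -0.286. A window ending at relative week +1 gives 0.

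**Direct fit.** Fitting the pooled regression to noise-free data (3 lotteries × 18 zip codes × 15 weeks = 810 rows) gave the same values, whether each control zip code has one effect overall or one per stacked lottery.

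**Check of the remedy.** On relative weeks -5 to +1 (3 × 18 × 7 = 378 rows) the coefficient was 1.000d under every post-lottery profile and every common citywide trend tried. On random data it matched the mean of the three 2x2 estimates with five pre weeks to six decimals; the all-weeks coefficient did not.

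**Dropping post weeks alone.** Keeping 5, 7 and 9 pre weeks with one effect per control zip code gave 0.833d under a linear citywide fall of 0.5d per week, and 0.779d and 0.703d under falls of 10% and 20% per week from a level of 10d. The lottery weights became 0.927, 1.010 and 1.063. Stack-specific zip effects remove that trend bias but not the unequal weights (0.928, 1.010, 1.062).

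**Precision, in weekly SDs, independent weeks**

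- Plan, all weeks: √[(1/2 + 1/13)(18/17)/3] = 0.451.
- Balanced window: √[(1/2 + 1/5)(18/17)/3] = 0.497, about 10% larger.
- With the 17 controls' data treated as shared across lotteries: 0.447 and 0.493.

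**The case against.** The strongest reply is that the row set is not stated. The May-to-August dates describe data collection and the cross-city analysis. For the pooled fit the plan speaks of an event window and of combining per-zip results, and the preferred per-zip estimate uses only pre and lottery weeks. A stack limited to those weeks would have no bias. The zip-level figure is missing from the available text and might show a window. This stands as a reason for caution about size. However, the text never says the stack ends with the lottery weeks, and item 8 expects post-treatment points in the graphs, so a figure showing them would not settle the matter.

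The reach is also limited. Pooling is introduced as optional, the per-zip, city and county 2x2 estimates are untouched, and the event-study plots show post weeks separately. All true, but none of it changes the coefficient the plan names as its overall effect.

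The distortion may be modest against the noise. Under independent weeks, the balanced window lowers mean squared error only if the bias exceeds √(0.497² - 0.451²) ≈ 0.21 weekly SDs. That needs d above about 1.4 SDs under full harvesting, 2.7 under half, 1.8 under 25% carry-over and 0.45 under full carry-over. This is fair, and it is why the point does not rank higher. A coefficient whose meaning depends on post-lottery behaviour is still hard to interpret, whatever its variance.

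Finally, keeping all weeks and adding one selected-by-post term, with stack-specific zip effects, also recovers d under a common post shift, with an SE of 0.478 (about 6% above the plan). That is another sound route. Its single post term assumes the same shift after each lottery, and it does not reproduce the simple average of the per-zip estimates.

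**Conclusion.** The concern holds on the plain reading and should be fixed. The pooled coefficient is d minus 0.46 times the mean post-lottery shift if all 15 weeks are stacked, with a multiplier of -0.44 or -0.29 under the two shorter windows tried. It is unbiased only if the selected zip codes show no average post-lottery change relative to unselected ones, or if the stack ends with the lottery weeks. The direction is unknown: harvesting inflates and carry-over shrinks. The multipliers follow from the plan's calendar; the sizes in units of d rest on assumed scenarios. Confidence is medium because the window is unstated and the zip figure is unavailable. A separate substitution analysis under item 8 would not correct the pooled coefficient.

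**What to change.** 1. State which relative weeks enter the pooled fit.
2. Fit the headline pooled regression on five pre-treatment weeks and the two lottery weeks for each lottery (relative weeks -5 to +1), with zip effects specific to each stacked lottery. State that the per-zip 2x2 estimates also use five pre weeks; the pooled coefficient is then their simple average.
3. Do not just delete post weeks while keeping 5, 7 and 9 pre weeks with one effect per control zip code, because a citywide decline then biases the result.
4. Give item 8's substitution analysis a model: separate per-lottery fits with selected-by-treatment and selected-by-post terms. Report the post-lottery change with its interval, as secondary.

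The cost is one row filter and one added regressor in the per-lottery fits, with no new data. The headline SE rises about 10% if weeks are independent. The post-lottery change has SE √[(1/pre + 1/post)(18/17)], or about 0.59, 0.57 and 0.62 weekly SDs in the three lotteries, and 0.36 for their average when the controls' data are treated as shared, so it will be imprecise.

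### Data end 4 weeks after the last lottery, so the substitution that section 8 plans to measure is cut off at August 14 and its estimated size is truncated

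*Combined protocol and SAP*

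**What the plan says.** Section 5, item 1 fixes the calendar: "We will include data from May 2, 2021 through August 14, 2021 in this analysis". It splits the window into "5 weeks of pre-intervention, 6 weeks of intervention, and 4 weeks of" follow-up. Section 7 applies the same dates to every region, with collection "during the entire sweepstakes, and for 4 weeks after the conclusion of the sweepstakes". Section 4 describes a sweepstakes of at least six weeks, with one zip code drawn for each two-week round, and section 5, item 3 counts three selected zip codes.

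The preferred 2x2 estimates in section 5 compare pre-treatment averages with treatment-period averages, for example "the average vaccination rate during the treatment period for each zip code". Post-treatment weeks do not enter them.

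Section 8 raises the question at issue. Extra vaccinations may come from persuasion, or from "causing people who were eventually going to be vaccinated to move up their vaccination date". The plan would look for event-study points below zero after treatment and use an analysis like the main ones to estimate how large the substitution is. It names no expected shift length and no time horizon for that estimate.

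**The concern.** The question in section 8 has no time limit, because it concerns people who would have been vaccinated at any later date. The data do have one. Someone brought forward from August 10 lowers the count in the week of August 10 and contributes to a visible dip. Someone brought forward from September 10 lowers a week that is never collected. However well the post-period is analysed, the second person's dose stays in the apparent gain and the estimated substitution omits it.

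The fixed end date also gives the three selected zip codes different horizons. In the pooled event-time figure, post-weeks 1 to 4 contain all three zip codes, weeks 5 and 6 contain two, and weeks 7 and 8 contain one. At stake is how the result is described: whether a gain during the lottery can be called additional vaccination, and over what period.

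**Working it through.** **Calendar.** May 2 to August 14, counting both days, is 105 days. 105/7 = 15 weeks = 5 + 6 + 4, which reproduces the plan's split. The six lottery weeks therefore run from June 6 to July 17, and the post-period from July 18 to August 14.

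For the zip code in round k, the post-weeks are 15 − 5 − 2k:

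| Zip code | Treated | Post-weeks to August 14 | Post-weeks while later rounds still run |
|---|---|---|---|
| 1 | June 6 to 19 | 8 | 4 |
| 2 | June 20 to July 3 | 6 | 2 |
| 3 | July 4 to 17 | 4 | 0 |

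These dates assume exactly six weeks. The document gives six as a minimum. With the end date unchanged, an eight-week sweepstakes would leave 15 − 5 − 8 = 2 post-weeks.

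**What is fully visible.** The last lottery day is July 17. A dose brought forward by 4 weeks or less would otherwise have fallen on or before August 14. Its deficit is therefore in the data for every comparison.

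**What is cut off.** The document gives no shift length, so the following is a sensitivity calculation. Assume that the whole gain is displacement and that each shift is exponential with mean m weeks. Doses whose original date fell inside the treatment period have already cancelled in the treatment-period average. The net gain at the end of treatment consists of the others. Because the exponential has no memory, their remaining time is again exponential with mean m, whatever the length of the treatment period. With F weeks of follow-up, the share not yet offset is

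share = exp(−F/m).

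| Comparison | F | m = 2 | m = 4 | m = 8 | m = 12 |
|---|---|---|---|---|---|
| City, and zip code 3 | 4 | exp(−2) = 14% | exp(−1) = 37% | exp(−0.5) = 61% | exp(−0.333) = 72% |
| Zip code 2 | 6 | exp(−3) = 5% | exp(−1.5) = 22% | exp(−0.75) = 47% | exp(−0.5) = 61% |
| Zip code 1 | 8 | exp(−4) = 2% | exp(−2) = 14% | exp(−1) = 37% | exp(−0.667) = 51% |
| Any, with 12 weeks | 12 | exp(−6) = 0% | exp(−3) = 5% | exp(−1.5) = 22% | exp(−1) = 37% |

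The shape of the shift distribution matters too. If every shift were exactly 12 weeks, none of the deficit would fall before August 14 in any comparison. If shifts were uniform between 0 and 8 weeks, simulation gives unoffset shares of 27% for the city and 0%, 14% and 43% for zip codes 1, 2 and 3.

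**Dates for the fix.** July 17 + 84 days = October 9, which gives the third zip code 12 weeks. The first two reach 12 weeks on September 11 and September 25, so one pull covers all three. October 9 is 56 days, or 8 weeks, after August 14.

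**The case against.** The strongest reply is that the plan already anticipates the problem. It names harvesting, pre-registers a check, and nowhere says that the absence of a dip proves persuasion. Its preferred estimates are treatment-period effects and are not described as lasting. The question appears under additional items and applies only if a positive effect is found, and the form asks for no justification of the sample. All of this is fair, and it limits the point to the substitution estimate.

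A reader might infer that four weeks is simply too short to separate persuasion from moved-up dates, or that the plan counts everyone without a visible dip as persuaded. The document supports neither reading. The first depends on a shift length that is not given, and short shifts are fully covered. The second is a rule the plan does not contain.

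Two further objections stand in part. Any finite window truncates, and 12 weeks would still miss 37% of a purely displaced gain at a mean shift of 12 weeks. Also, each single-zip analysis has one treated unit and the document gives no variance, so the precision of a 12-week cumulative difference cannot be computed. These argue for reporting several horizons and labelling them; they do not remove the mismatch between question and window.

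Unequal follow-up is not a defect in itself. All three zip codes share the first four weeks, and the extra weeks for the first two add information.

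**Conclusion.** The point holds as a limit on what section 8 can deliver. Its substitution estimate covers only doses brought forward from dates up to August 14, and the plan does not say so. A dip would support displacement, but no dip would leave later displacement open.

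The size is conditional. Nothing is missed if shifts are 4 weeks or less. Under full displacement with exponential shifts averaging 8 weeks, the unoffset share is 61% for the city and the third zip code, 47% for the second and 37% for the first. These figures concern timing only; full displacement is an extreme case, and none of them is the bias of a planned estimate.

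Truncation makes measured substitution too small. It does not follow that the long-run effect is overstated overall, because people prompted by the lottery but vaccinated after August 14 would be missed as well. The main treatment-period estimates are unaffected.

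**What to change.** Keep May 2 to August 14 for the main treatment-period estimates. For the section 8 question only:

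- Pull the same routine weekly series from the health department and the CDC through October 9, 2021. If the sweepstakes runs beyond six weeks, move this date so that the last zip code still has 12 weeks.
- Report the selected-minus-unselected difference in cumulative first doses per resident, counted from the start of each zip code's lottery, at 4, 8 and 12 weeks after that lottery ends. Use equal horizons for all three zip codes. This nets later deficits against the gain.
- Treat the randomised zip code comparison as the main evidence on substitution and the city and county versions as supportive.
- State the horizon in any conclusion, and say that no dip within it does not establish persuasion. This wording is worth adopting even if no further data are collected.

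The cost is one later data pull and one table. The substitution result arrives about 8 weeks later, and the later weeks are noisier and more open to other influences, especially in the non-randomised comparisons.
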